#### 4.0 OBJECTIVE(S) & HYPOTHESIS

Obstructive sleep apnea (OSA) has been estimated to affect between 2 and 4% of the U.S. population < Young T, NEJM 1993>. It is a serious, lifethreatening condition associated with obesity, hypertension, congestive heart failure, pulmonary hypertension, coronary artery disease, and cardiac arrhythmias and has an 8 year mortality rate of nearly 40% <Parrish JM, Mayo Clin Proc 2004, He J, Chest 1988>. Following general anesthesia, patients with OSA have been noted to have a significantly increased risk of respiratory complications, morbidity and mortality <Gupta RM Mayo Clin Proc 2001, Liao P, Sleep 2007, Young T, Sleep 2007, Marshall NS, Sleep 2008 >. This may be due to residual effects of inhaled anesthetics which can decrease upper pharyngeal muscle tone leading to airway compromise in OSA patients <Bell RL, Anes Clin of NA 2005>. Also, OSA patients are exquisitely sensitive to the ventilatory depressant effects of postoperative opioids, causing decreased responsiveness to hypercarbia and episodic arterial hypoxemia <Ostermeier AM, Anes Anal 1997, Stoelting, Anesthesia and Coexisting Disease 4th ed>. Currently, there is not a well-established, general anesthetic technique that will decrease the risk of complications in OSA patients. The objective of this study is to compare the postoperative recovery profile of OSA patients receiving

standard Sevoflurane inhaled anesthesia versus Sevoflurane combined with a low-dose ketamine infusion.

We hypothesize that the group of obstructive sleep apnea patients that receive low-dose intraoperative ketamine will report lower pain scores, require less supplemental intravenous Morphine, and have less frequent side effects and desaturation episodes post-operatively than the group receiving saline.

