Anesthesia will be maintained in the both groups with inhaled Sevoflurane starting at 4% end-tidal concentration and titrated to keep the bispectral index (BIS) value at 40-50 (Bispectral Index, Aspect Biomedical, Natick, MA). After induction and before surgical incision is made, patients will receive an intravenous bolus saline or the study drug, S(+) ketamine 0.5mg/kg IBW bolus followed by a continuous infusion of 0.5 mg/kg/hr (IBW) using a Baxter syringe pump. The infusion will be stopped at the closure of the abdominal fascia layer, approximately 30 minutes before the end of surgery. In both groups, neuromuscular blockade will be maintained with rocuronium and titrated to train-of-four (TOF) ratio until the abdominal fascia is closed. Oxygen, air (no nitrous oxide), IV fluids, vasoactive drugs, and fentanyl (up to 5mcg/kg IBW) will be titrated at the anesthesiologist's discretion to maintain hemodynamics at 25% of baseline. Glycopyrolate and neostigmine will be given to facilitate reversal of neuromuscular blockade. Sevoflurane will be discontinued immediately prior to completion of surgery. All patients will receive IV ketorolac 30mg at conclusion of closure of abdominal fascia. Endotracheal tube will be removed when patient meets extubation criteria (spontaneous breathing with min 6ml/kg IBW tidal volume, following commands with ability to sustain hand grip and 5-sec head lift). All patients will then be discharged from the operating room to the post-anesthesia care unit (PACU).

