Upon arrival in the PACU, all patients will be monitored according to standard post-anesthesia protocols for a period of at least 2 hours. The PACU nurse that is blinded to treatment group will assess and record baseline vital signs including HR, BP, RR, SpO2, and VRS score. Modified Aldrete score including presence of nausea/vomiting, sedation level or evidence of dysphoria will be recorded at 15 minute intervals. SpO2 will be monitored continuously with documentation of oxygen flow required to maintain oxygen saturation of at least 94%. As per PACU protocol, initially patients will receive oxygen 40% by open face mask, with weaning to NC or RA, maintaining SpO2 > 94%. Desaturation episodes will be scored automatically by pulse oximetry analysis software (Nellcor, NPB-290). Data evaluated will include: comparison of patient demographics, time to first analgesic, number of analgesic demands, amount of analgesic consumed in the OR and PACU, frequency of side effects, and ODI (oxygen desaturation index). ODI is defined as the number of desaturations (lower than 4% from baseline) per hour of recording, which correlates with PSGdetermined apnea/hypopnea index and can be used as an indicator of postoperative apneic episodes <Ahmad S, Anesthesia and Analgesia 2008>}. Time to first analgesia request will be recorded and pain (VRS >/= 4) will be treated with intravenous morphine 2mg. This will be repeated at 5 minutes intervals until pain score improves or patient has untoward side

effects, at which time the PACU physician should be immediately called to the patient's bedside. Further monitoring for of patients in PACU or on the floor may be indicated in some patients according to the discretion of the attending anesthesiologist and surgeon; however it is not mandatory for this study. According to Terris et al., "Significant complications [of OSA] generally emerge within 2 hours after surgery. Therefore a decision regarding the level of postoperative monitoring needed may be made with confidence during the period of time that the patient is in the recovery room" <Terris DJ, Laryngoscope 1998>.

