# 11.0 STATISTICAL CONSIDERATIONS

Statistical analysis with *a priori* power analysis was performed to determine the number of patients per group sufficient to detect a decrease of >30% in postoperative opioid requirements on the basis of the results of Kararmaz et al., Anesthesia and Analgesia 2003. With a power of 80% and a type 1 error of 5%, it was estimated that 32 patients will be required per group. We will plan to enroll 65 patients total to account for unanticipated subject dropout. Mann-Whitney U-test will be used to compare VRS, modified Aldrete, and patient satisfaction scores. Student's t-test will be used to compare BMI, time to first analgesic, number of analgesic demands, amount of analgesic consumption and ODI. The X2 test will be used to compare frequency of side effects, race and sex distribution. The resulting values will be expressed as mean +/- SD or median and range with P< 0.05 considered statistically significant.

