# 16. Protocol Procedures, Methods, and Duration of the Study—in nontechnical language

- Participants in this study will be randomized to two groups: One group will receive an intravenous (IV) dose of ketamine during the surgery. The other group will receive a normal saline placebo IV (control group). For the patients that are randomized to the ketamine group, the PI will submit an order for the ketamine to the research pharmacist. The pharmacist will determine the dosing of ketamine based on a standard calculation and prepare the syringe that will be used to dispense the ketamine. For both groups, the IV infusion will be discontinued at the conclusion of the surgery. Participants will receive standard anesthetic drugs and appropriate pain medication to control their postoperative pain in keeping with the current practice. We will compare recovery data including vital signs and pain scores as well as potential side effects of controlled versus study group. Approximately 24 hours after surgery, a patient assessment form will be completed ("24 Hr Post-Operative Data Collection Form") by the PI or research study team.
- b. What is the probable length of time required for the entire study (i.e., recruitment through data analysis to study closure)?
  Approximately two years
- Participants will be involved during surgery, during their recovery in the PACU, and at one time point approximately 24 hours postoperatively (to complete the Post-Operative Patient Satisfaction Assessment Form).
- d. If different phases are involved, what is the duration of each phase in which the participants will be involved? If no phases are involved, enter "not applicable." Not applicable
- **e.** List the procedures, the length of time each will take, and the frequency of repetition, and indicate whether each is done solely for research or would already be performed for treatment or diagnostic purposes (routine care) for the population. *Insert additional table rows as needed.*

Procedure	Length of Time	Frequency of	Doscorrah (Dos)
rioccarc			Research (Res) -
	Required of	Repetition	OR- Routine Care
	Participants		
Pregnancy testing for women of	<5 minutes	once	□Res ⊠Routine
childbearing potential			
Weight measurement	<5 minutes	once	□Res ⊠Routine
Normal Saline or Ketamine infusion	<three hours<="" td="">once	⊠Res □Routine	</three>	once	⊠Res □Routine
Monitoring and measurement of	From onset of	Continuously	□Res ⊠Routine

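### Time to first analgesic is assigned a t-test with no rule for patients who have no event in PACU; a comparison of recorded times alone would probably understate any delay

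*Combined protocol and SAP*

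**What the plan says.** Section 11.0, with the same text in Section 5.0, assigns the test: "Student's t-test will be used to compare BMI, time to first analgesic, number of analgesic demands, amount of analgesic consumption and ODI".

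The outcome is collected under Section 8.0. The data to be evaluated include "time to first analgesic, number of analgesic demands, amount of analgesic consumed in the OR and PACU", and the section adds: "Time to first analgesia request will be recorded and pain (VRS >/= 4) will be treated with intravenous morphine 2mg". The setting is the PACU, where "all patients will be monitored according to standard post-anesthesia protocols for a period of at least 2 hours". For 24 hours, Section 8.0 lists morphine usage but not the time of a first dose or request. Item 16 of the re-opened submission says: "Approximately 24 hours after surgery, a patient assessment form will be completed"; the fields of that form are not shown.

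No section gives a value for a patient who has no event in PACU, or says whether that patient is omitted, given a set time or censored. The withdrawal criteria (Sections 6.0 and 13.0, Item 19) do not cover the case. Section 8.0 names the outcome in two ways, first analgesic and first analgesia request, and states no time origin, although it introduces the PACU assessments from arrival there.

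On direction, Section 4.0 expects that ketamine patients "will report lower pain scores, require less supplemental intravenous Morphine".

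**The concern.** A t-test needs a number for every patient it includes. A patient who never needs analgesia in PACU has none, so unless a rule is written down the natural default is to analyse the recorded times only. That conditions on having had the event. Because ketamine is hypothesised to reduce morphine need, it may also raise the share of patients with no event, and the patients lost would then be those who did best. Both the estimated delay and the chance of detecting it would shrink.

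Without a rule, the choice between omitting and keeping these patients could also be made after the data are seen, and the two analyses can differ a good deal.

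**Working it through.** **The plan's own figure.** The 32 per group concerns a fall of more than 30% in opioid requirement, not this outcome. No SD is given, so it can only be back-solved. From n = 2(SD/Δ)²(1.96 + 0.84)², with Δ = 0.30 × control mean and n = 32, SD = 0.30 × √(32/15.7) ≈ 0.43 × control mean (two-sided). That neither confirms nor refutes 32, and the point below does not depend on it.

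**Inputs.** From the documents: 32 per group and 5% type 1 error (Section 11.0; taken as two-sided, since sidedness is not stated), and a minimum PACU stay of 2 hours (Section 8.0). Assumed, because the documents give no event times: exponential times, the medians below, and recording that ends at τ = 120 or 180 min.

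**Formulas.** For median m, the mean is μ = m/ln 2 and the event-free share is S = 2^(−τ/m).
- Restricted mean to τ: R = μ(1 − S)
- Mean of recorded times only: C = (R − τS)/(1 − S)

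**Worked case, 30 v 60 min, τ = 120.**
- Control: μ = 43.28, S = 2⁻⁴ = 0.0625, R = 43.28 × 0.9375 = 40.58, C = (40.58 − 7.5)/0.9375 = 35.28.
- Ketamine: μ = 86.56, S = 2⁻² = 0.25, R = 86.56 × 0.75 = 64.92, C = (64.92 − 30)/0.75 = 46.56.
- Restricted difference: 64.92 − 40.58 = 24.3 min. Recorded-only difference: 46.56 − 35.28 = 11.3 min.

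**Across cases.** Power is simulated at 32 per group with 3,000 to 10,000 trials per case; separate runs agree to within about 2 points.

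| Medians (min) | τ (min) | Expected event-free per 32 (C v K) | Restricted → recorded-only difference (min) | Power: recorded-only t | Power: t, event-free set to τ |
|---|---|---|---|---|---|
| 10 v 15 | 120 | 0 v 0.1 | 7.1 → 6.8 | 31% | 32% |
| 10 v 20 | 120 | 0 v 0.5 | 14.0 → 12.6 | 71% | 75% |
| 15 v 30 | 120 | 0.1 v 2 | 19.0 → 14.1 | 59% | 75% |
| 20 v 40 | 120 | 0.5 v 4 | 22.1 → 13.6 | 45% | 74% |
| 30 v 60 | 120 | 2 v 8 | 24.3 → 11.3 | 27% | 68% |
| 15 v 30 | 180 | 0 v 0.5 | 21.0 → 18.8 | 72% | 76% |
| 30 v 60 | 180 | 0.5 v 4 | 33.1 → 20.4 | 45% | 74% |

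At τ = 120, a restricted-mean test has 76, 77, 75 and 69% power for the four doubled-median cases, and log-rank 76, 77, 76 and 71%. The t-test with event-free patients set to 120 min is close to both. This is expected: when everyone is observed for 2 hours, it compares the same restricted means.

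**Waning effect.** Section 8.0 says: "The infusion will be stopped at the closure of the abdominal fascia layer, approximately 30 minutes before the end of surgery". Item 16 says: "For both groups, the IV infusion will be discontinued at the conclusion of the surgery". The two differ on the moment and should be reconciled, but on either the infusion is off before PACU, so the effect may fade. With the event rate halved at first and then equal (τ = 120):
- Control median 15 min, effect for 30 min: difference 10.7 → 10.4 min; power 48% recorded-only, 48% restricted mean, 44% log-rank.
- Control median 30 min, effect for 45 min: 15.8 → 13.5 min; 40, 43 and 34%.
- Control median 30 min, effect for 60 min: 19.0 → 15.7 min; 48, 55 and 46%.

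**If ketamine only prevents requests.** With 10% v 30% event-free and identical times among the rest, the restricted difference is about 17 min and the recorded-only difference about 0.

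**Larger trial.** At 75 per group (150 in Item 15, 1:1 assumed), power for recorded-only v restricted mean is 98% v 99% at 10 v 20 min, and 52% v 96% at 30 v 60 min.

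**The case against.** The strongest reply is that the harm is conditional and may be slight. Section 2.0 expects most patients to need IV opioids after major surgery. Two hours is a minimum stay, and the plan does not say recording stops there; at 180 min the 15 v 30 case loses only about 4 points of power. The doubled medians have no source in the documents. A smaller delay (10 v 15 min) loses almost nothing, and the waning cases lose 0 to 7 points. All of this stands, and it limits the size. It does not remove the problem: 30 v 60 min still loses heavily at 180 min, and none of these arguments supplies the missing rule.

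Four stronger readings are tempting and are not supported.
- That the plan drops event-free patients: it names a test and is silent on who enters it.
- That the t-test itself is the fault: with every patient kept, it retains most of the power.
- That the trial's power is about 27%: the sample size rests on opioid requirement, and this is one of several other outcomes.
- That morphine is given whether or not the patient asks: Section 8.0 does not say. First analgesic and first request may be loose wording for one event, but the text does not settle it.

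**Conclusion.** The concern holds in a limited form. The plan assigns a t-test to a time-to-event outcome collected in PACU and leaves patients without the event unaddressed. An analysis of recorded times alone would probably understate a delay, because it selects on something ketamine is expected to change.

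The size depends on the share of event-free patients, which the documents do not give. It runs from negligible to a loss of more than half the estimated delay (24.3 to 11.3 min), with power falling from about 69% to about 27% in the heaviest exponential case tabulated. The assumptions are the exponential times, the chosen medians, and recording that ends at 120 or 180 min. The consequence is confined to this one comparison. It should be fixed before the data are seen; confidence in the size is medium.

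**What to change.** In Sections 5.0 and 11.0, take this outcome out of the t-test list and state:
- the event, either first request or first morphine dose, but one of them;
- the origin, PACU arrival;
- that patients without the event by 2 hours are censored at 2 hours;
- that the groups are compared by the difference in 2-hour restricted mean time with its 95% CI, shown with Kaplan-Meier curves;
- that the number event-free at 2 hours is reported per arm.

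Log-rank is a possible alternative, but it had the least power in the waning cases, so one test should be named in advance. If the t-test is preferred, the minimum is a sentence keeping every patient in the comparison, with those event-free at 2 hours set to 120 min.

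The cost is one or two sentences and slightly more analysis work. No new data are needed. Events after 2 hours are not used in this comparison.

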#### 8.0 STUDY INTERVENTIONS/PROCEDURES

This is a prospective, randomized, double-blind, placebo-controlled single institution study. All patients will be provided written informed consent in the preop clinic prior to participation. Patients will be randomly allocated to the ketamine (K) study group or the control (C) group. Random allocation of patients will be performed by study coordinator using closed envelopes containing allocation group. All patients will be provided standard hospital care.

On the day of surgery, baseline oxygen saturation measurements will be recorded for each patient. The study coordinator will provide the attending anesthesiologist with a 30ml syringe containing either ketamine (K) 10mg/ml or saline (C). Both syringes will be labeled "Ketamine 10mg/ml" along with time and date of preparation by the pharmacy. In the operating room, standard ASA monitors will be used along with arterial and /or CVP monitoring according to the preference of the attending anesthesiologist. After adequate preoxygenation with 100% oxygen, general anesthesia will be induced with intravenous midazolam 2mg, fentanyl 100mcg and propofol, 2-3 mg/kg ideal body weight (IBW) followed by rocuronium 50mg before endotracheal intubation. IBW is calculated by the Hamwi Formula: men start with 106 lbs for first 5 feet + 6 lbs for each inch over 5 feet,

women use 100 lbs for first 5 feet + 5 lbs for each inch over 5 feet (Medium frame); for small frame (- 10%), large frame (+ 10%).

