Describe your ability to obtain access to the proposed population that will allow recruitment of the necessary number of participants:
All patients scheduled for the above surgical procedure will be seen preoperatively in the PAC at TKC and Highlands. The opportunity to participate will be offered at such time.

Describe the inclusion/exclusion criteria:

Inclusion criteria: aged 19-100, scheduled to undergo general ENT or Orthopedic Surgery.

Patients should have a diagnosis of obstructive sleep apnea as confirmed by sleep study or deemed high risked for obstructive sleep apnea by clinical predictors (greaterthan 4 clinical predictors of obstructive sleep apnea as described by STOP BANG).

Exclusion criteria: positive pregnancy test, ASA> III, history of alcohol or narcotic abuse in last 90 days, significant cardiovascular or respiratory disease (baseline oxygen saturation below 92%), significant psychiatric or neurologic disease, history of significant hepatic or renal disease (baseline creatinine>1.5), history of allergy or contraindication to anesthetic agents or ketamine including patients with increased ICP, increased IOP, severe arrhythmias, history of delirium, hallucinations, or psychosis, or history of uncontrolled seizures, or potential risk for malignant hyperthermia (family history), history of difficult intubation that would preclude standard induction of anesthesia, prisoners, persons who are mentally impaired, and non-English speakers.

- **d.** If participants will comprise more than one group or stratification, describe each group (e.g., treatment/intervention, placebo, controls, sham treatment) **and** provide the number of participants anticipated in each group.

  Participants will be randomly assigned to either the low-dose Ketamine infusion group or the normal saline infusion group. The two groups will comprise the study population, n=150.
- e. Indicate which, if any, of the special populations listed below will be involved in the protocol. Include the Special Populations Review Form (SPRF) if indicated.

  □ Pregnant Women: Attach SPRF—Pregnant Women, Fetuses, Neonates/Nonviable Neonates

□ Fetuses: Attach SPRF—Pregnant Women, Fetuses, Neonates/Nonviable
Neonates
□ Neonates/Nonviable Neonates: SPRF—Pregnant Women , Fetuses ,
Neonates/Nonviable Neonates
□ Prisoners: Attach SPRF—Prisoners
☐ Minors (<18 years old): Attach SPRF—Minors
⋈ Employees or students at institution where research conducted

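### Baseline tests on BMI, race and sex answer no useful question, and the opioid and ODI comparisons make no planned use of baseline data already collected

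*Combined protocol and SAP*

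**What the plan says.** Section 11 (Statistical Considerations) is the only analysis plan in the documents; section 5 repeats it. It assigns one test to each variable and mixes baseline and outcome variables in the same lists: "Student's t-test will be used to compare BMI, time to first analgesic, number of analgesic demands, amount of analgesic consumption and ODI", and "The X2 test will be used to compare frequency of side effects, race and sex distribution". One threshold covers everything: "The resulting values will be expressed as mean +/- SD or median and range with P< 0.05 considered statistically significant".

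No regression, covariate, stratified analysis or stratified randomisation is described. Section 8 allocates by closed envelope and names no stratification factor. No rule says what follows a baseline P value below 0.05.

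Baseline information is nevertheless available. BMI, race and sex are to be compared, age is an eligibility item, the type of surgery is known from scheduling, and section 8 says: "On the day of surgery, baseline oxygen saturation measurements will be recorded for each patient". That section also defines an ODI event as a fall relative to baseline, so baseline saturation enters that endpoint, though not as a covariate.

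The sample size in section 11 is 32 per group, 65 in total, for laparoscopic gastric bypass. The Human Subjects Protocol for the re-opened study (item 15) has a different population, described as general, ENT or orthopedic surgery and in one place as any surgery under general anaesthesia. It also has a different size: "The two groups will comprise the study population, n=150". It gives no new analysis plan and no new power calculation.

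**The concern.** If allocation is properly randomised, any difference in BMI, race or sex between arms is due to chance. A significance test on it therefore tests a hypothesis already known to be true. Whether an imbalance matters depends on how strongly the variable predicts the outcome and how large the difference is, and a baseline P value does not measure that. With no planned response, any reaction to a flagged variable would be chosen after seeing the data, and an unflagged but prognostic imbalance would stay in the estimate.

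The outcome comparisons have the complementary gap. If age, surgery type, BMI or starting saturation predict opioid use or ODI, a model containing them gives a narrower interval and removes the part of the difference that comes from chance imbalance. The wider case mix of the re-opened study makes both more relevant, because mixed procedures may add outcome variation that a two-sample t-test leaves in the error term.

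**Working it through.** **Inputs.** From section 11: power 80%, type I error 5%, 32 per group, a decrease of more than 30%. From Human Subjects Protocol item 15: 150 in total, taken as 75 per arm (the ratio is not stated). Assumed because the documents are silent: a two-sided test, the coefficient of variation (CV) of opioid use, and R², the share of outcome variance explained by the covariates.

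**1. The plan's own figure.** The plan states: "With a power of 80% and a type 1 error of 5%, it was estimated that 32 patients will be required per group". No SD is given, so 32 can only be back-solved. Normal approximation: d = (1.960 + 0.842) × √(2/32) = 0.70. With the t distribution, d = 0.71. A 30% decrease then implies a CV of 0.30/0.71 ≈ 0.42. The CV matters: by the normal approximation, 0.50 needs 44 per arm and 0.60 needs 63.

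**2. Baseline tests.** Three tests at 5%, if independent: 1 − 0.95³ = 0.143. Correct randomisation would still produce at least one significant baseline difference in about 14% of trials.

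**3. Is the unadjusted t-test valid?** Yes, on average. In simulation (20,000 trials per setting, 32 or 75 per arm, covariate–outcome correlation r of 0.2, 0.3 or 0.5) its type I error was 4.7% to 5.2%, and that of ANCOVA was similar. In the subset of trials where the covariate happened to be imbalanced at P < 0.05, the t-test's error at 32 per arm was about 7%, 10% and 18% for r = 0.2, 0.3 and 0.5. That is the risk from chance imbalance.

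**4. Power with adjustment, including the cost of estimating covariates.** For k covariate terms and N patients in total, the variance is multiplied by (1 − R²) × [1 + k/(N − k − 3)]. The test has N − 2 − k degrees of freedom and noncentrality d√(n/2) divided by the square root of that factor.

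At 32 per arm, d = 0.71, k = 2: the cost factor is 1 + 2/59 = 1.034. Unadjusted noncentrality is 0.7115 × 4 = 2.846. At R² = 0 it becomes 2.846/√1.034 = 2.80; at R² = 0.2 it becomes 2.846/√(0.8 × 1.034) = 3.13.

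| Terms at 32 per arm | R² = 0 | 0.1 | 0.2 | 0.3 |
|---|---|---|---|---|
| k = 2 | 79% | 83% | 87% | 91% |
| k = 3 | 78% | 82% | 86% | 90% |
| k = 4 | 77% | 81% | 86% | 90% |

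The unadjusted reference is 80%. Break-even is at R² of about 0.03, 0.05 and 0.07 for k = 2, 3 and 4. Surgery type in three categories uses two terms, so surgery type plus age is the k = 3 row.

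**5. At 75 per arm.** With k = 2 the cost factor is 1 + 2/145 = 1.014, and d = 0.30/CV.

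| CV | Unadjusted | R² = 0 | R² = 0.1 | R² = 0.2 |
|---|---|---|---|---|
| 0.42 | 99.1% | 99.0% | 99.5% | 99.8% |
| 0.60 | 86.0% | 85.6% | 89.0% | 92.2% |
| 0.80 | 62.6% | 62.0% | 66.6% | 71.7% |

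At R² of 0.1 to 0.2 the gain is under 1 point at CV 0.42, about 3 to 6 points at CV 0.6, and about 4 to 9 points at CV 0.8.

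**The case against.** The strongest reply is that nothing here is invalid. Randomisation justifies the unadjusted t-test, the simulated error rate confirms it, and the plan attaches no action to a baseline P value, so the baseline tests change no outcome analysis. The documents give no correlation between any baseline variable and opioid use or ODI, so a gain from adjustment cannot be demonstrated. With covariates that predict nothing, adjustment costs a little power. At 150 patients and the CV implied by section 11, power is already 99%.

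All of that stands, and it rules out several stronger readings that a reader might infer:

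- *That precision is certainly being thrown away.* This needs an R² that the documents do not give, and below about 0.03 (two terms, 32 per arm) there is nothing to gain.
- *That the gain equals the simple 1/√(1 − R²) increase in standardised effect*, which would give 84%, 88% and 92% at R² of 0.1, 0.2 and 0.3. That ignores the cost of estimating the covariates.
- *That the plan mishandles imbalance.* It does not handle it at all; there is no conditional adjustment to criticise.
- *That baseline saturation goes unused.* It defines the ODI event; it is only absent as a covariate.

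The reply does not rescue the baseline tests, which remain uninformative. Nor does 150 patients dispose of the precision argument: the 99% rests on a CV back-solved from a gastric bypass calculation, and the re-opened study enrols a more mixed population whose variability is not stated.

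**Conclusion.** The point holds as one of efficiency and protection against chance imbalance, not as an error in the t-test. Significance tests on BMI, race and sex serve no purpose in this randomised comparison, and under correct randomisation about 14% of trials would show at least one flag if the three tests are independent.

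The benefit of adjustment is plausible but not guaranteed. With two covariate terms at 32 per arm it ranges from a loss of about 1 power point at R² = 0 to a gain of about 11 at R² = 0.3. At 75 per arm it is negligible if the CV is near 0.42 and worthwhile if the CV is 0.6 or more; the loss when covariates predict nothing is under 1 point. These figures assume a two-sided test, 1:1 allocation, a true 30% decrease and the stated R² values. They are worked for opioid amount; the documents give no effect size for ODI, so its gain cannot be quantified. Adjustment does not resolve the missing SD or the unreconciled totals of 65 and 150.

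**What to change.** 1. Remove the tests on BMI, race and sex from sections 5 and 11. Show these variables descriptively by arm, without P values.
2. Make the main analysis of opioid amount and of ODI a pre-specified linear model with arm plus a short covariate list chosen on prognostic grounds and fixed before unblinding. Examples are surgery type and age for opioid amount, and surgery type, BMI and day-of-surgery SpO2 for ODI. State how surgery type is categorised, and keep the number of terms small.
3. Report the adjusted difference with its 95% CI, and keep the unadjusted t-test as a sensitivity analysis.
4. State that the covariate list will not change in response to observed baseline differences.

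The cost is plan wording and a slightly longer analysis program. The covariates come from screening, scheduling or the day of surgery, so no new data collection is needed. The statistical downside is the small power loss given above if the chosen covariates turn out not to be prognostic.
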